### 10.5 VISIT SCHEDULE FOR THE PILOT TRANSFUSION TRIAL

Approximately 36 patients with WAIS III-PIQ scores  $\leq 90$  will be asked to participate in Phase II of the study. Half of these patients will be randomized to undergo a chronic transfusion regimen for six months, and the other half will be treated with standard care alone, guided by their disease symptoms.

During the first visit for Phase II, subjects who completed Phase I and went on to Phase II will sign informed consent, be screened for eligibility (including a blood draw for the hematology and chemistry panels), and will have their quality-of-life assessed by the self-administered SF-36. As described above, this can occur at the Visit 4 Debriefing or at a subsequent visit. The SF-36 assesses eight health concepts: 1) limitations in physical

activities because of health problems; 2) limitations in social activities because of physical or emotional problems; 3) limitation in usual role activities because of physical health problems; 4) bodily pain; 5) general mental health (psychological distress and well-being); 6) limitations in usual role activities because of emotional problems; 7) vitality (energy and fatigue); and 8) general health perceptions.

If > 6 months (but < 1 year) have passed since the subject's participation in Phase I of the study, the subject must FIRST repeat the WAIS-III PIQ portion of the Neuropsych Battery at the first visit of Phase II to confirm that the subject's PIQ score is  $\leq 90$ . If the score is still consistent with eligibility requirements, the study coordinator will complete the screening blood draw on the subject, administer the SF-36, and will schedule a repeat MRI so that the image can be compared to the MRI conducted during Phase I. The site will locally confirm that the repeat MRI does not contain any new neurological findings when compared to the Phase I MRI.

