clinic visits to complete the interval history form, have blood drawn to measure Hb and ferritin levels, and for completion of a chemistry panel.

Within two weeks of the patient's final transfusion or clinic visit at month 6, the SF-36 will be re-administered in addition to the NP test battery. Within two weeks of this visit, another visit must occur and the patient will complete the MRI. The neuropsychological testing will again take about 6 to 6½ hours to complete, and the MRI will take approximately 30 minutes to complete.

The last visit of Phase II is for the Exit Debriefing. Once all of the tests have been completed, the patient will meet with a doctor or nurse to review a summary of the results and ask any questions he/she may have. It is possible that the tests used in this study (the NP questionnaires or the MRI) may show problems in the functioning of the patient's brain. If there are any problems, the patient will receive specific recommendations about what should be done. If requested by the patient, this information will be sent to his or her primary care doctor and will include recommendations for follow-up care.

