## 10.6 LABORATORY ANALYSES

Each transfusion will be preceded by measurement of Hb S, A, F, A2, and other, Hct, red cell antibody screening, and Hb concentration.

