### 11.2 CLINICALLY SIGNIFICANT LABORATORY ABNORMALITIES

All laboratory measurements will be evaluated for abnormalities. An abnormal laboratory finding is not by itself considered to be an AE or SAE unless the investigator considers the abnormal finding to be of clinical significance and should be reported in such a manner. The abnormal laboratory finding does not have to be associated with the use of the study product to be considered clinically significant.

For any significant changes noted by the investigator to be clinically significant or those that meet the criteria above, the clinical significance and relationship to the administration of study product will be established. This assessment will be recorded on the CRF. If the changes are clinically significant, the investigator will continue to

monitor the subject until the parameter returns to baseline or until the investigator determines that follow-up is no longer medically necessary.

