### 11.8.3 ADVERSE EVENTS

Six months after the first subject is enrolled in the study, and at the end of each 6 months thereafter, a semi-annual statistical analyses and review of all AEs will occur. The SDMC will:

- Use the current version of the MedDRA dictionary to code all AEs that have been recorded on study AE forms.
- Make a “snapshot” copy of the AE data, including MedDRA codes.
- Create frequency tables of treatment x occurrence (yes or no, since inception of the study) of all patients. One table will be created for each highest-level MedDRA term for which AEs have been reported. The counting units are patients, not events.
- Compute the FET statistic to test the alternative hypothesis that occurrence of AEs is not independent of treatment group. The FET p-value is not adjusted for multiplicity.
- If the FET p-value is less than the critical value shown in Table 11.3 and the active treatment group has a higher AE rate, the SDMC will conduct further statistical analyses as indicated by the circumstances and alert the DSMB to this finding in the semi-annual DSMB report.
- Collaborate with the Principal Investigator to incorporate the results into the study’s semi-annual report to the DSMB and the NHLBI Project Officer.

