Individuals randomized to the treatment arm will receive simple transfusions and additional blood testing every 3 to 4 weeks. A blood sample will be sent to the study laboratory before each transfusion. Individuals randomized to the treatment arm will receive the same general care for SCD as those who are not randomized to treatment.

Individuals randomized to the standard care arm will have monthly contact with clinic staff to complete an interval history form, and to have blood drawn (at Months 3 and 6) for a Hematology and Chemistry panel and to measure ferritin levels. All patients will be taught the signs and symptoms of stroke and asked to report any such signs.

After 6 months of treatment, both groups will complete another NP Battery and SF-36. A new MRI must be completed within 2 weeks after the NP Battery.

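### A repeat chemistry panel is scheduled at Months 3 and 6 only in the standard-care arm, so chemistry-detected adverse events are looked for systematically only in controls

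*Protocol*

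**What the plan says.** **Standard-care arm.** Section 10.5 schedules in-person visits at Months 3 and 6 at which these patients "have blood drawn to measure Hb and ferritin levels, and for completion of a chemistry panel". Section 14.2 (Phase II visits) says the same of this arm: monthly contact, and "to have blood drawn (at Months 3 and 6) for a Hematology and Chemistry panel and to measure ferritin levels".

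**Transfusion arm.** Section 10.6 lists the laboratory work: "Each transfusion will be preceded by measurement of Hb S, A, F, A2, and other, Hct, red cell antibody screening, and Hb concentration". Section 11.5 adds ferritin at entry (if the value on file is over three months old), Month 3 and end of study, without limiting it to one arm. Section 14.2 says only: "Individuals randomized to the treatment arm will receive simple transfusions and additional blood testing every 3 to 4 weeks". It does not say what that testing contains. The arm also "will receive the same general care for SCD as those who are not randomized to treatment".

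**Screening.** For patients coming from Phase I, section 10.5 requires that they "be screened for eligibility (including a blood draw for the hematology and chemistry panels"). The creatinine exclusion in section 9.3 implies a screening chemistry value for every Phase II entrant.

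**Link to the safety comparison.** The AE definition in 11.1.1 includes abnormal laboratory findings. Section 11.2 states: "All laboratory measurements will be evaluated for abnormalities", and makes an abnormal value an AE only if the investigator considers it clinically significant. Section 11.8.3 instructs the data center: "Compute the FET statistic to test the alternative hypothesis that occurrence of AEs is not independent of treatment group". There is one table for each highest-level MedDRA term, and patients are counted rather than events. Table 11.3 sets the alert at p < 0.01, unadjusted, and only when the active arm has the higher rate.

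**The concern.** A between-arm comparison of AE occurrence assumes that events have a similar chance of being found in each arm. For abnormalities that show only on a chemistry panel, the protocol as written does not provide this. Controls are tested twice after randomization. Transfused patients have a baseline value and no scheduled follow-up.

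The alert works in one direction only. Finding such events in controls raises the control count, and not looking for them in transfused patients keeps the active count low. Both effects work against the only pattern that can trigger an alert.

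The protocol itself treats these analytes as relevant. Creatinine is an exclusion criterion in 9.3, and Table 11.2 lists reduced kidney function, renal insufficiency and renal failure among expected conditions. Section 11.8.1 says that abnormal laboratory measures will be monitored for imbalance between the arms. The separate laboratory analysis for the DSMB (11.8.5) names only hemoglobin and ferritin, so it would not pick up a missed chemistry signal.

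**Working it through.** The protocol states no figure on this point, so there is nothing to reproduce. The check has three steps.

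**1. Scheduled tests after randomization, side by side**

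| Test | Standard care | Transfusion |
|---|---|---|
| Chemistry panel | Months 3 and 6 (10.5, 14.2) | none listed |
| Hb | Months 3 and 6 | before each of 6 to 8 transfusions |
| Ferritin | Months 3 and 6 | Month 3 and end of study (11.5) |
| Hb fractions, Hct | Hct only as part of the hematology panel in 14.2, if included | before each transfusion (10.6) |
| Antibody screen | none listed | before each transfusion (10.6) |

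Section 13.1 gives 36 randomized, so 18 per arm, with 15 per arm expected to complete. Scheduled chemistry panels are 18 × 2 = 36 in standard care and 0 in the transfusion arm.

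**2. What the alert requires**

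Take *a* affected transfusion patients and *c* affected controls in one MedDRA term, and apply the two-sided Fisher exact test at p < 0.01 with the active arm higher. With c = 0 and n per arm, p = 2·C(n, a)/C(2n, a).

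- n = 18, a = 6: 2 × 18,564 / 1,947,792 = 0.0191, no alert.
- n = 18, a = 7: 2 × 31,824 / 8,347,680 = 0.0076, alert.
- n = 15, a = 7: 2 × 6,435 / 2,035,800 = 0.0063, alert.

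The smallest *a* that gives an alert:

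| Affected controls | 18 per arm | 15 per arm |
|---|---|---|
| 0 | 7 (p = 0.0076) | 7 (p = 0.0063) |
| 1 | 9 (p = 0.0072) | 9 (p = 0.0052) |
| 2 | 11 (p = 0.0045) | 10 (p = 0.0078) |

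One or two controls whose event was found on a panel that only they receive raise the requirement by two to four transfused patients.

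**3. Illustration of lost alert probability**

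The protocol gives no chemistry-AE rates, so the rates here are assumptions. Let a fraction *s* of such events be detected in the transfusion arm and all of them in standard care, with all falling in one term. The probability of an alert is the sum of Bin(a; n, s·p_T) × Bin(c; n, p_C) over all (a, c) that meet the alert rule.

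| True rates, transfusion / standard | n per arm | s = 1 | s = 0.75 | s = 0.5 | s = 0 |
|---|---|---|---|---|---|
| 50% / 10% | 18 | 0.40 | 0.15 | 0.03 | 0 |
| 50% / 10% | 15 | 0.30 | 0.09 | 0.01 | 0 |
| 60% / 10% | 18 | 0.65 | 0.29 | 0.06 | 0 |
| 60% / 10% | 15 | 0.54 | 0.20 | 0.03 | 0 |
| 40% / 5% | 18 | 0.36 | 0.13 | 0.02 | 0 |
| 40% / 5% | 15 | 0.22 | 0.07 | 0.01 | 0 |

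In these scenarios, losing a quarter of the events in the transfusion arm cuts the alert probability by more than half. The column s = 0 is a limiting case and not a description of the trial, because events can also be found outside the schedule.

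**The case against.** Four points can be made on the other side.

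**Events can still surface.** A reader might infer that chemistry-based AEs cannot be found in transfused patients. The protocol does not support that. Interval histories capture hospitalizations, emergency visits and clinical events in both arms (11.5), the transfusion arm keeps the same background care, and the content of its additional blood testing in 14.2 is left open. This stands: the events are not systematically looked for, which is different from being undetectable.

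**Other asymmetries run the opposite way.** A reader might also infer that the whole AE comparison is biased toward no alert. That is not shown. The transfusion arm has 6 to 8 in-person contacts against two visits and four calls, and it alone has scheduled antibody screens. These can raise its counts for other terms. Because each MedDRA term has its own table, only terms that hold chemistry findings are tilted as described. This stands, but extra contacts elsewhere do not correct the tilt in those terms.

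**The alert is not the DSMB's only view.** AEs go to the DSMB every six months whether or not an alert fires, and transfusion reactions are reported regardless of incidence (11.8.3, 11.8.4, Table 11.3). This stands. However, regular reports can show only events that were detected.

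**A panel count is not a bias.** 36 against 0 counts procedures, and any effect on alert probability rests on assumed rates. Even with equal schedules, an alert needs at least 7 of 18 transfused patients (39%) in one term. This also stands and limits the practical weight of the point.

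**Conclusion.** The point holds in a limited form. The protocol schedules post-randomization chemistry for standard care only, in two places, and the transfusion arm's itemized tests contain none. Because clinically significant laboratory abnormalities are AEs and the alert requires a higher rate in the transfusion arm, unequal ascertainment makes an alert less likely for MedDRA terms holding chemistry findings. Each of the first two controls so detected raises the requirement by about two transfused patients.

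This rests on reading the 10.6 list and the ferritin rule in 11.5 as the transfusion arm's full on-study schedule. If the unspecified testing in 14.2 was meant to include chemistry, the fault is one of wording, and the passages still need to agree. How much alert probability is lost cannot be derived from the protocol. The net direction across all AE terms is not established. The efficacy analysis of PIQ change is unaffected.

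**What to change.** Reconcile sections 10.5, 10.6, 11.5 and 14.2 so that both arms follow one stated post-baseline chemistry schedule, and say in 14.2 what the transfusion arm's additional blood testing contains. Which schedule is adopted is for the sponsor and investigators to decide. The statistical requirement is that it be the same in both arms.

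If the common schedule has two panels per patient, the cost is about 18 × 2 = 36 panels in the transfusion arm and a text edit. Blood is already drawn before each transfusion, and ferritin is already due at Month 3 and end of study, so no extra visit is needed.

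If the schedules stay unequal, keep all AEs in the 11.8.3 tables and add a second version that leaves out AEs detected only by the control-arm scheduled chemistry panel. This requires the AE record to show how the event was found. Do not restrict laboratory-triggered AEs to analytes scheduled in both arms: that would drop antibody-screen findings, which are scheduled only in the transfusion arm and bear directly on transfusion harm.

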## 10.6 LABORATORY ANALYSES

Each transfusion will be preceded by measurement of Hb S, A, F, A2, and other, Hct, red cell antibody screening, and Hb concentration.

## 10.7 TIMETABLE

The first three months will be used for standardization of NP and MRI studies at the institutions. During Months 6 to 18, all subjects will be enrolled into the cross-sectional study and will complete the MRI and NP battery. Concurrently, a subset of patients will be randomized to transfusion or standard care. By 24 months, all patients randomized to transfusion will have completed their six months regimen. When the last of these patients complete his/her second NP battery and MRI, the database will be finalized, and statistical analysis will follow.

Enrollment into Phase I was closed on February 22, 2008. The inclusion/exclusion criteria and the study procedures were modified so that patients willing to participate in 6 months of transfusion therapy can participate in Phase II, but still complete the baseline NP Battery and MRI previously obtained from Phase I.

**Phase I:**

	Visit One	Visit Two/Visit Three	Visit Four
Consent	X		
Eligibility Screening	X		
History and Physical Exam	X		
MMSE	X		
POMS	X		
PSS	X		
Neuropsychological Battery 		X	
MRI Testing 		X	
Exit Debriefing			X

1. Enrollment into Phase I was completed on February 22, 2008.
2. The sequencing of the Neuropsychological Battery and the MRI is flexible, and either component can occur at Visit 2. The component that is not completed at Visit 2 will occur at 3.

**Phase II – Original**

	Eligibility Visit 	Transfusion Visits  or Phone Calls/Visits 	NP Battery and SF-36 Visit	MRI Testing Visit	Exit Debriefing Visit
Consent	X				
Eligibility Screening	X				
SF-36	X				
Randomization	X				
Transfusions 		X			
Phone Calls/Clinic Visits 		X			
SF-36			X		
Neuropsychological Battery 			X		
MRI Testing 			X		
Exit Debriefing					X

**Phase II timetable for subjects who were never enrolled in Phase I (or who completed Phase I more than 1 year ago):**

	Eligibility Visit 	Visit 2 MRI	Visit 3 NP Battery/ Randomization	Transfusion Visits  or Phone Calls/Visits 	NP Battery and SF-36 Visit	MRI Visit	Exit Debriefing Visit
Consent	X						
Eligibility Screening	X						
PIQ	X						
MMSE	X						
POMS	X						
MRI Testing		X				X	
SF-36 Neuropsychological Battery (Randomization)			X		X		
Transfusions  Phone Calls/Clinic Visits 				X			
Exit Debriefing							X

**1** Patients must meet inclusion/exclusion criteria based on their Hemoglobin and Ferritin values, and their scores on the POMS and PIQ before an MRI and the NP Battery are administered.

**2**Number of transfusions during the six-month period will vary between six and eight, and will occur at 3- to 4-week intervals.

**3** Phone calls will occur during Months 1, 2, 4, and 5. In-person clinic visits occur during Month 3 and Month 6.

## 11 SAFETY MANAGEMENT

### 11.1 ADVERSE EVENTS (AEs) AND SERIOUS ADVERSE EVENTS (SAEs)

The investigator is responsible for the detection and documentation of events meeting the criteria and definition of an AE or SAE as provided in this protocol. Since the cross-sectional neurocognitive/MRI phase of the study is observational only, AEs and SAEs will not be collected. However, AEs and SAEs will be collected for all subjects participating in the transfusion intervention pilot study.

#### 11.1.1 DEFINITION OF AN ADVERSE EVENT

An AE is defined for this study as any untoward medical occurrence in a subject who is administered clinical study material. The occurrence of this event does not necessarily have a causal relationship with study product. An AE can therefore be any unfavorable and unintended sign (including an abnormal laboratory finding), symptom, or disease temporally associated with the use of a study product, whether or not related to the study product.

Examples of an AE include:

- Exacerbation of a chronic or intermittent pre-existing condition, including either an increase in frequency or intensity of the condition
- Significant or unexpected worsening or exacerbation of the condition/indication under study
- A new condition detected or diagnosed after study product administration even though it may have been present prior to the start of the study
- Pre- or post-treatment events that occur as a result of protocol-mandated procedures (e.g., invasive protocol-defined procedures, modification of a subject's previous drug treatment regimen).

An AE does not include:

- Medical or surgical procedures (e.g., colonoscopy or biopsy). The medical condition that leads to the procedure is an AE
- Social or convenience hospital admissions where an untoward medical occurrence did not occur
- Day-to-day fluctuations of a pre-existing disease or conditions present or detected at the start of the study that do not worsen

### 11.1.2 DEFINITION OF AN SAE

An SAE is any adverse drug experience occurring at any dose that:

- Results in death
- Is life-threatening (at risk of death at the time of the event)
- Requires inpatient hospitalization or prolongation of existing hospitalization

*NOTE: Complications that occur during hospitalization are AEs. If a complication prolongs hospitalization or fulfills any other serious criteria, the event is serious. Hospitalization for elective treatment of a pre-existing condition that did not worsen from baseline is not considered to be an AE.*

- Results in disability/incapacity

*NOTE: The term disability is defined as a substantial disruption of a person's ability to conduct normal life functions. This definition is not intended to include experiences of relatively minor medical significance, such as uncomplicated headache, nausea, vomiting, diarrhea, influenza, or accidental trauma (i.e., sprained ankle) that may interfere or prevent everyday life functions but do not constitute a substantial disruption.*

- Is a congenital anomaly/birth defect
- Important medical events that may not result in death, be life-threatening, or require hospitalization may be considered an SAE when, based upon appropriate medical judgment, they may jeopardize the patient or subject and may require medical or surgical intervention to prevent one of the outcomes listed in the above definition

### 11.2 CLINICALLY SIGNIFICANT LABORATORY ABNORMALITIES

All laboratory measurements will be evaluated for abnormalities. An abnormal laboratory finding is not by itself considered to be an AE or SAE unless the investigator considers the abnormal finding to be of clinical significance and should be reported in such a manner. The abnormal laboratory finding does not have to be associated with the use of the study product to be considered clinically significant.

For any significant changes noted by the investigator to be clinically significant or those that meet the criteria above, the clinical significance and relationship to the administration of study product will be established. This assessment will be recorded on the CRF. If the changes are clinically significant, the investigator will continue to

monitor the subject until the parameter returns to baseline or until the investigator determines that follow-up is no longer medically necessary.

### 11.3 ASSESSMENT OF ADVERSE EVENT SEVERITY

The investigator will make an assessment of intensity for each AE and SAE reported during the study. The assessment will be based on the investigator's clinical judgment. The intensity of each AE and SAE should be assigned to one of the following categories:

Mild: Awareness of sign, symptom, or event, but easily tolerated; does not interfere with usual daily activities or tasks

Moderate: Discomfort enough to cause interference with usual daily activity; may warrant therapeutic intervention

Severe: Incapacitating; inability to perform usual activities and daily tasks; significantly affects clinical status; requires therapeutic intervention

Life-threatening: AE is life-threatening

Death: AE causes death

An AE that is assessed as severe should not be confused with an SAE. Severity is a category used for rating the intensity of an event; both AEs and SAEs can be assessed as severe. An event is described as 'serious' when it meets one of the pre-defined outcomes as described in "Definition of an SAE" section of this protocol.

